- iv. There is no significant difference in means between the pre-test among the newly employed nurses (NEN) among interventional and the control groups in all dependent variables.
- v. There is a significant mean difference between PRE-SBLST and all POST-SBLST results among NEN in all dependent variables.

Study Design

The study design was a prospective, longitudinal, single-blind basic experimental design, randomized control trial (RCT) design.

Study Location

The study was carried out in Jordan; Amman and Al-Zarqa City. The accessible population was NEN in five hospitals. The researchers selected three Jordanian hospitals. The selection was according to the capacity, capability of the institution and eligibility criteria. Computer-generated randomization (Random Allocation Software, version 1.0) was applied in blocks to allocate the hospitals by distributing them into two arms. The first arm was the control group; selected from three hospitals; Prince Hamza Hospital, AL-Basheer Hospital, and AL-Zarqa Governmental Hospital (n=51); the second arm was the interventional group from two hospitals; Prince Faisal Governmental Hospital and Dr.Jameel AL-Totanji Hospital.

Randomization of the Hospitals

To prevent data contamination between the control and interventional groups, computer-generated randomization (Random Allocation Software, version 1.0) was applied in blocks to allocate the hospitals by distributing them into two arms. The first arm was the control group; selected from three hospitals; Prince Hamza Hospital, AL-Basheer Hospital, and AL-Zarqa Governmental Hospital (n=51); the second arm was the interventional group from two hospitals; Prince Faisal governmental hospital and Dr.Jameel AL-Totajji hospital. The control and interventional groups were selected from different hospitals because the researchers are always worried about data contamination and try to minimize it between the control and intervention groups; if the sample was selected from the same area and both groups worked closely together, the data would be contaminated.

Inclusion Criteria

The researchers tried to maintain homogeneity and minimize any variations among the participants by

1. selecting both interventional and control groups from newly employed nurses
2. Male and female participants
3. Participants only who understand the questionnaires and interventions in English

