Adult half-body manikin and a pediatric full-body manikin are necessary; with lung bag inflation and deflation characteristics, palpable carotid pulse, the chest includes spring inside to facilitate chest recoil, and chest compression board, bag-valve-mask-ventilation, chest compression performed on the Charlie simulator to relieve choking. The principles investigator (PI) had a master's degree in critical care nursing, eighteen years of experience between ICUs, lecturers and clinical instructors, valid BLS and ACLS, training of trainers in nursing education, and randomized control trial training. The facilitator must have CPR certifications in BLS and ACLS, enough expertise in education and training, and good communication skills the investigator had a master degree in critical care. Two research assistants supported the

PI in collecting data; one research assistant for the control group and the other for the interventional group.

Post-test

All participants completed the immediate post-test-1 after the interventions. The post-test-2 was conducted by providing the participants with a Google Form Platform link through their phone and email addresses. The post-test after three months evaluates whether the participants' level stayed at the same level or minimized by comparing the mean value between all post-tests. Forty-eight participants in the experimental group completed post-test-2 with a response rate of 94%, and 45 participants in the control group with a response rate of 88%.

Sample Size Estimation

Sample size calculation is performed by using G*POWER software (version 3.1); sample size calculation is summarized and consists of the following steps (1) Select the test family (F-test family), (2) Select the statistical test (Select ANOVA-repeated test, between factors), the preliminary test analysis the researchers used in this study, the rationale for using the Select ANOVA-repeated test between factors due to measure many dependent variables means at different time points. (3) The parameters selected to calculate sample size include one side tail, alpha (α) and equals (0.05)- type one error, Power (P) and equal (0.8), effect size, the number of groups is two (each group = $n/2$) n = the estimated sample size, number of measurements were four measurements (Pre-test, Post-test immediately, Post-test after two months, and Post-test after three months).

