Effect Size (ES) = 0.26, automatically calculated by G*Power software, depending on the sample size of the previous study, the effect size is calculated, the

Control group's post-test result $M \pm SD$ was equal (25.03 ± 3.04) with a sample size of 28 participants, and the interventional group (26.64 ± 2.64) with sample size 29 participants. The sample size is 72 participants; because the research study continued for three months, we added a 10% drop rate for each month, so the drop rate is 30%. Final sample size estimation including drop rate ($n \setminus (1 - \text{dropout rate}) = 72 / (1 - 0.30) = 102$ participants, the intervention group arm is 51 participants, and The largest sample size was obtained from the interventional group, more than the Control Group and the Control group arm 51 participants.

Simple Random Sampling of the Participants

After obtaining ethical approval and permission to conduct the study from the Ministry of Health in Jordan, approval letter (Education/Info\ 15177) and ethical approval letter (MOH/REC/2022/340), The researchers started the formal face-to-face visits to arrange with the nursing director and a continuous education office in the selected hospitals about the study objective and how the study would proceed; The researchers received the activation letter to initiate the study and prepared the list of the available participants who met the study's eligibility criteria. The number of participants depends on the availability of newly employed nurses in the institution who meet the inclusion criteria. The researchers randomly selected the participants from the participants' list by randomly sampling from newly employed nurses in each hospital for interventional and control groups.

. The response of the control group hospitals was as the following; the nursing director and continuous education in AL-Zarqa Governmental Hospital responded by providing all the information about participants and selecting a time and day to perform the Pre-test, standard treatment and the immediate post-test. Prince Hamzah Hospital and AL-Basheer Hospital gave the researcher the names of departments in the

hospital, including those with NEN, and we visited these departments to select the available NEN randomly and performed Pre-test, standard treatment, and immediate post-test in their departments.

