DEVELOPMENT, VALIDATION, AND
EVALUATION OF THE EFFECTIVENESS OF
SIMULATION IN BASIC LIFE SUPPORT TRAINING
(SBLST) ON NEWLY EMPLOYED NURSES IN
GOVERNMENTAL JORDANIAN HOSPITALS

Statistical Analysis Plan

Last update On 20-4-2023

Malaysian Human subjects protection review board date: 20-4-2023

Statistical Analysis Plan

Introduction

The data will be collected through the Google Forms platform, and the researchers will extract the data responses from Google Forms as an Excel sheet (Microsoft Office 2016); all the quantitative data will be coded and transferred to IBM SPSS version 27; the data will be analyzed by using (1) descriptive and (2) inferential statistic.

1. Descriptive Statistics

The descriptive statistic will illustrate the homogeneity and characteristics of NEN in the control and experimental group, including the number and percentage of participants for each group. Also, it will be used to describe statistics for participants' knowledge, practice and confidence level mean percentage in the pre-test and post-test scores.

2. Inferential Statistics

A. Independent T-test

Independent T-test will be used to identify the homogeneity or heterogeneity between pre-tests and post-tests in the control and experimental groups in all dependent variables by interpreting the *P*-value and comparing means (SD). The researchers plan to use independent T-tests despite the normality assumption not being fulfilled depending on the central limit theorem, which states that if samples are more than 30 participants in each group, the researcher can use mean and SD.

B. Repeated Measures-ANOVA

The researchers will use "Repeated Measurement ANOVA" for inferential statistics of the mean of the dependent variables between the interventional and comparator groups in all pre-test and post-tests. Finally, the researchers compared the

*

“Mean,” “Standard Deviation,” and significant level (*P*-value) between tests to explore the effectiveness of the intervention SBLST.

In this step of the analysis, the researchers want to estimate a good idea about the outcomes and how SBLST is considered a good intervention or not after comparing the knowledge score, practice score, and confidence level in both interventional and control groups. The researchers selected a *P*-value < 0.05 for statistical analysis significant to accept the alternative hypothesis or reject the null hypothesis.

C. Effect Size (Cohen’s Score)

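### Pre-test comparability is judged by a t-test P-value with no tolerance limit, and no planned analysis conditions on the pre-test score whatever that test shows.

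*SAP*

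**What the plan says.** Protocol, Research Hypotheses, item iv: "There is no significant difference in means between the pre-test among the newly employed nurses (NEN) among interventional and the control groups", for every dependent variable. The Protocol's Objective makes the same prediction.

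SAP, section 2A, supplies the test: "Independent T-test will be used to identify the homogeneity or heterogeneity between pre-tests and post-tests". The judgement is to come from the P-value together with a comparison of means (SD). The same section applies unadjusted t-tests to the post-tests. The only numerical threshold in the SAP for any test is P < 0.05 (section 2B).

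SAP, section 2B, plans a repeated-measures ANOVA of the "mean of the dependent variables between the interventional and comparator groups in all pre-test and post-tests". The pre-test is thus one of the repeated outcomes, not a covariate. No model term is named as deciding. The Protocol's Sample Size Estimation chose "Select ANOVA-repeated test, between factors".

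SAP, section 2C, adds Cohen's d from pre-test to post-test-2 within each arm, and between arms after the intervention.

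Neither document gives an equivalence margin, a limit on the standardised difference, or an action if the arms differ at pre-test.

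**The concern.** Hypothesis iv is a null hypothesis that the plan hopes to support. A non-significant result is not evidence of equality, and at this sample size the test leaves room for sizeable gaps. If the report then presents the arms as comparable, readers will take the unadjusted post-test difference as the effect of the simulation training, although part of it may be a starting difference.

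The design gives reason for care. Hospitals, not nurses, were allocated, three to control and two to intervention (Protocol, Randomization of the Hospitals). Nurses were also reached by different routes. In two control hospitals the team visited departments, while the intervention hospitals arranged available nurses on scheduled days (Protocol, Simple Random Sampling of the Participants).

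**Working it through.** **Inputs from the Protocol (Sample Size Estimation).** Alpha 0.05; power 0.80; effect size f = 0.26; four measurements; 72 nurses before dropout; 30% dropout; 51 per arm. Source study: control 25.03 ± 3.04 (n = 28), intervention 26.64 ± 2.64 (n = 29).

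**Assumptions, not in the documents.** Two-sided t-test (the SAP gives no sidedness); pre/post correlation r = 0.5, with range 0.3 to 0.7; equal SDs at each test; nurses independent unless stated.

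**1. The plan's own figure.** f = (1.61/2)/3.04 = 0.265, printed as 0.26. With an assumed correlation of 0.5 among four measurements, the noncentrality is 0.2648² × 72 × 4 / (1 + 3 × 0.5) = 8.08, and power is 0.800 at N = 72. Then 72/0.70 = 102.9, against the stated 102. The sample size reproduces and is not part of this point.

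**2. Planning difference in SD units.**
- Pooled SD = √[(27 × 3.04² + 28 × 2.64²)/55] = 2.84, so d = 1.61/2.84 = 0.57.
- On the control SD, d = 1.61/3.04 = 0.53.

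**3. Largest non-significant observed gap.** t(0.975, 100) × √(2/51) = 0.393 SD, which is 0.393/0.566 = 69% of the pooled planning difference. With the 48 and 45 completers at post-test-2 the limit is 0.412 SD.

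**4. Chance that a true gap gives P > 0.05** (noncentral t, 51 per arm):

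| True gap (SD) | Non-significant |
|---|---|
| 0.2 | 83% |
| 0.3 | 68% |
| 0.4 | 48% |
| 0.5 | 29% |

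A true gap of about 0.55 SD is needed for 80% power to detect it.

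**5. What a 0.3 SD gap does to each analysis when there is no treatment effect.** The post-test t-test carries r × gap. The between-group ANOVA effect over pre-test, post-test-1 and post-test-2 carries (gap + 2 × r × gap)/3. A change or group-by-time contrast carries r × gap − gap.

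| r | Post-test t-test | ANOVA between groups | Change / group-by-time |
|---|---|---|---|
| 0.3 | 0.09 | 0.16 | −0.21 |
| 0.5 | 0.15 | 0.20 | −0.15 |
| 0.7 | 0.21 | 0.24 | −0.09 |

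For the t-test at r = 0.5, 0.15/0.57 = 26% and 0.15/0.53 = 28% of the planning difference. These biases assume that the gap between arms carries forward at the same rate as differences between nurses within an arm. A stable difference between hospitals could carry forward more fully.

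**6. An observed gap of 0.39 SD, just inside the limit.** The conditional type I error of the post-test t-test is 7.6%, 12.5% and 19.8% at r = 0.3, 0.5 and 0.7.

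**7. Effect of allocating hospitals.** With equal hospital sizes, the chance variance of the baseline difference is (1 − ICC) × 2/51 + ICC × (1/3 + 1/2). At assumed ICCs of 0, 0.01, 0.05 and 0.10 its SD is 0.20, 0.22, 0.28 and 0.34. The t-test ignores this, so its P-value does not describe chance imbalance correctly when the ICC is above zero.

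**8. With the pre-test as covariate.** Under a linear model the bias in step 5 becomes zero. At r = 0.5 the standard error of the arm difference falls from 0.198 to 0.198 × √(1 − 0.25) = 0.171 SD, again ignoring clustering.

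**The case against.** A reader might infer that the plan contains a formal rule under which P > 0.05 declares the arms homogeneous and so switches off adjustment. The documents do not say that. SAP section 2A also compares means (SD), and no later analysis depends on the pre-test P-value. Adjustment is absent in every case, so the P-value is not what produces the bias. This objection stands. The comparison of means is still no safeguard, because no limit is attached to it.

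A reader might also apply the 0.15 SD bias to the whole plan. It belongs to the post-test t-tests only. The repeated-measures ANOVA, on which the sample size rests, includes the pre-test. Its between-group effect averages the gap in, and a group-by-time contrast errs in the opposite direction. This stands too, but because the deciding term is not named, the ANOVA cannot be relied on to remove the gap.

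Nor do the documents show that imbalance occurred. They state random selection in the hospitals and restrict eligibility to keep nurses similar, and they give no baseline data. The different routes and the five allocated hospitals make imbalance a risk, not a finding.

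The figures depend on choices. The sample-size text mentions a one-sided test. On that reading the limit is 0.33 SD, and a true 0.3 SD gap in the tested direction is missed 56% of the time. That is smaller, but the conclusion is the same.

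Finally, deleting hypothesis iv and the pre-test t-test would change no treatment estimate. That is right: the covariate adjustment carries the benefit, and the rewording only prevents a misleading claim of comparability.

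**Conclusion.** The point holds in this limited form. Non-significance at 51 per arm cannot show that the arms start level, since observed gaps up to 0.39 SD pass and a true 0.3 SD gap passes 68% of the time. Nothing in the plan conditions on the pre-test whatever that test shows. A 0.3 SD gap would move the unadjusted post-test t-test by 0.15 SD (0.09 to 0.21), about a quarter of the planning difference. The direction and size of the error in the ANOVA depend on a term that the SAP leaves open.

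The figures rest on two-sided tests, independent nurses and assumed correlations. The change is worth making because the pre-test score is already collected, and using it removes this source of bias under a linear model and usually gains precision.

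**What to change.** - **SAP, sections 2A and 2B.** Compare each post-test between arms with the pre-test score of the same outcome as a covariate (ANCOVA or an equivalent mixed model), regardless of the baseline difference. Name this arm comparison as the deciding one.
- **SAP, sections 1 and 2A.** Replace the pre-test significance test with means, SDs and standardised differences by arm and by hospital.
- **Protocol, Objective and Research Hypotheses iv.** Restate the expectation of no significant pre-test difference as a description of baseline, not a hypothesis to be tested.

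The cost is wording in both documents and one extra model term, with no new data. The Protocol's Post-test section already reports post-test-2 completion (48 and 45 nurses), so the change should be dated and justified, saying whether outcome data had been examined. Adjustment for the pre-test does not solve the separate problem of drawing inference from five allocated hospitals.

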4. Participants who were previously on-seat undergraduate nursing students last two years, 2020 (4th year nursing bachelor level) and 2021 (3rd year nursing bachelor level) in the period of COVID-19 pandemic and receive basic and clinical learning by online method, and now became a newly employed nurse (NEN) in hospitals and delivered care to the patient.
5. Participants can attend five to seven hours of SBLST session.
6. For more control, we selected nurses who rarely face CPR and do not attend BLS raining the last two years.

Exclusion Criteria

1. The researchers excluded the NEN participants working in intensive care units because ICU nurses face CPR and perform BLS daily.
2. Excluded participants with medical or physical health problems (e.g., pregnant women and participants complaining of lower back pain).
3. Participants who attended CPR training less than two years previously were also excluded. Finally,
4. NEN who upgraded their educational degree from a diploma to a bachelor's degree were excluded.

Research Instruments

The study consists of a pre-test, intervention, immediate post-test-1 after the intervention, and finally, the post-test-2 three months after the intervention. This study measured knowledge, practice, and confidence through pre- and post-tests in control and experimental groups. This study used two interventions: SBLST for the interventional group and AHA-BLS 2020 brochure as a standard treatment for the control group. Data collection proceeded using the Google Form Platform (A web-based instrument Copyrighted by Google application).

The evaluation process includes a pre-test and two follow-up assessments to measure knowledge, practice and confidence. The researcher will analyse the means of each test; the total dependent variables were 30 questions listed in.

Languages of the Tools

According to the HCP educational level, all four sections of the tools assessment are written in English; furthermore, the researchers' assistance clarified any misunderstanding points or need for translation to the participants.

Tools Sections

The tools consist of five sections; research information sheet and consent forms, demographical data, knowledge assessment tools, skills assessment tools, and confidence level assessment tools.

Research information sheet and Consent Forms

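### With no missing-data rule, the planned repeated measures ANOVA would probably keep only the 93 of 102 nurses with all three tests and drop nine nurses' observed scores

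*SAP*

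**What the plan says.** The protocol (Research Instruments) sets three assessments: a pre-test, then "immediate post-test-1 after the intervention, and finally, the post-test-2 three months after the intervention". Its Post-test section states: "All participants completed the immediate post-test-1 after the interventions". The same section says post-test-2 went out as an online form link by phone and email, and reports: "Forty-eight participants in the experimental group completed post-test-2 with a response rate of 94%, and 45 participants in the control group", a control rate of 88%. It will judge retention by asking "whether the participants' level stayed at the same level or minimized by comparing the mean value between all post-tests". The Sample Size Estimation section puts 51 nurses in each arm.

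The SAP says in its Introduction that "all the quantitative data will be coded and transferred to IBM SPSS version 27". Section 2.A plans independent t-tests on the pre-tests and post-tests. Section 2.B states: "The researchers will use 'Repeated Measurement ANOVA' for inferential statistics of the mean of the dependent variables between the interventional and comparator groups", and applies this to every pre-test and post-test. Neither document names the SPSS procedure, a mixed model, imputation, an analysis population or a rule for nurses who did not return post-test-2.

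**The concern.** Classical repeated measures ANOVA, which in SPSS is the GLM repeated measures procedure, needs a complete row for each person. A nurse without post-test-2 then leaves the analysis at every time point, including the two at which she was tested. This has three consequences:

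- The ANOVA describes completers only, and the plan does not say so.
- The t-tests in section 2.A can use all 102 nurses at pre-test and post-test-1, so the same scores could be reported on 102 nurses in one table and 93 in another.
- If the chance of replying depends on a nurse's score, completer means are shifted. The arm contrast is shifted too when the two arms lose different fractions. Retention is also affected, because it is a comparison of post-test-1 with post-test-2.

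**Working it through.** **Inputs.** Arms of 51 and 51 (protocol, Sample Size Estimation); post-test-2 completers 48 and 45, with post-test-1 complete (protocol, Post-test); three outcomes and three time points (protocol, Research Instruments).

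**1. The protocol's own rates.** 48/51 = 94.1% and 45/51 = 88.2%. Both agree with the stated 94% and 88%.

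**2. Who is lost.** SBLST 51 − 48 = 3 (5.9%); control 51 − 45 = 6 (11.8%); total 9 of 102 (8.8%), leaving 93. Fisher's exact test of 3/51 against 6/51 gives p = 0.49.

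**3. What is discarded.** 9 nurses × 2 observed tests × 3 outcomes = 54 scores. Recorded scores total (102 + 102 + 93) × 3 = 891, so 54/891 = 6%.

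**4. Possible bias.** The documents give no scores by response status, so this is an illustration. Assumptions: normal scores with SD 1; the log-odds of non-response rise by 1.5 for each SD lower on post-test-1; correlation 0.6 between the post-tests; non-response of 6/51 and 3/51. The post-test-2 shift is 0.6 × the post-test-1 shift, and the change is their difference.

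| Shift in completer mean (SD) | Control | SBLST | SBLST minus control |
|---|---|---|---|
| Post-test-1 | +0.14 | +0.08 | −0.07 |
| Post-test-2 | +0.08 | +0.05 | −0.04 |
| Change, post-test-1 to post-test-2 | −0.06 | −0.03 | +0.03 |

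The contrasts are taken before rounding (0.075 − 0.141 = −0.066; 0.045 − 0.085 = −0.039). The control mean is raised more, so the contrast moves against SBLST. Selection on post-test-1 raises that test more than the later one, so change among completers looks worse than it was in both arms.

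**5. If raw means of all available nurses are compared instead.** Post-test-1 then uses all 51 per arm and has no shift, while post-test-2 uses responders and is raised by about 0.08 SD (control) and 0.05 SD (SBLST). Retention now looks better than it was.

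**6. An upper limit for same-direction loss.** If exactly the lowest post-test-1 scorers are missing, the completer mean rises by φ(z_p)/(1 − p). For p = 6/51 this is 0.224 SD, for p = 3/51 it is 0.125 SD, and the contrast error is 0.224 − 0.125 = 0.10 SD.

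**7. Scale.** The means and SDs in the protocol's sample-size section give d = (26.64 − 25.03)/2.84 = 0.57. The post-test-2 error of 0.04 SD is about 7% of that. It is also about one fifth of the contrast's standard error, √(1/48 + 1/45) = 0.21 SD.

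**8. What an all-data model recovers.** If non-response depends only on observed scores, as in step 4, using the observed post-test-1 scores brings the post-test-2 error to below 0.002 SD. If instead it depends on post-test-2 itself, with the same settings, the completer contrast is off by about 0.07 SD and the all-data estimate by about 0.05 SD. Only about 30% is removed.

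**The case against.** Several objections have force.

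- **Case deletion is inferred.** The SAP names SPSS 27 but no procedure, and SPSS also offers a mixed model. That is correct. But the named method is repeated measures ANOVA and no other rule is given, so completers only is the natural result of following the text.
- **The loss is small and was allowed for.** The protocol budgeted for 30% dropout, actual loss is 8.8%, and 93 exceeds 72. This answers a concern about power. It does not answer one about bias.
- **The imbalance may be chance.** A reader might infer from 6 against 3 that control nurses were truly less likely to reply. A difference of three nurses does not support that.
- **Equal selection cancels.** If both arms lost the same fraction in the same way, the arm contrast would be unaffected. Here the fractions differ, and the change within each arm is affected in either case.

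A reader might also infer that the ANOVA flatters retention. Under selection on post-test-1 it does the reverse; the flattering direction arises only if raw means of unequal sets are compared. The retention sentence in the protocol does not say which comparison is meant. Finally, a reader might expect larger errors. If low scorers drop out in one arm and high scorers in the other, the same settings give about 0.2 SD at post-test-1 (0.14 + 0.08), but nothing in the documents shows selection that differs by arm.

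**Conclusion.** The point holds as a matter of possible bias and unused data. Run as the classical procedure, section 2.B analyses 93 of 102 nurses and drops nine who have observed scores, without saying so and without a sensitivity analysis. Under the stated assumptions the arm contrast is off by about 0.07 SD at post-test-1 and 0.04 SD at post-test-2, against SBLST, and change among completers is off by about −0.06 SD (control) and −0.03 SD (SBLST). These sizes rest on an assumed link between score and reply that the documents neither show nor exclude. They are modest against d = 0.57 and do not suggest that the trial's conclusion would reverse. The point should still be corrected, because a better analysis is available in the same software at little cost.

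**What to change.** In SAP section 2.B, make the main analysis a linear mixed model for repeated measures (SPSS MIXED, REML, unstructured covariance, categorical time, group-by-time interaction), fitted to every observed score of all 102 nurses in their allocated arm. Take the post-test-1 to post-test-2 retention contrast from this model, and amend the retention sentence in the protocol's Post-test section to say so. The planned ANOVA may stay as a secondary analysis labelled as completers only. That is reasonable because the protocol, which carries the same date as the SAP, already reports the post-test-2 counts, so follow-up was complete when the plan was dated.

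The model removes the bias only if non-response depends on observed scores. Therefore add one sensitivity analysis that shifts the nine missing post-test-2 scores by 0 to 1 SD, separately by arm. As a guide to its reach, a 1 SD shift in both arms in the same direction moves the post-test-2 contrast by 6/51 − 3/51 = 0.06 SD, and in opposite directions by 9/51 = 0.18 SD.

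The cost is a change of SAP wording, slightly more analysis work and less familiar output, with no new data. Allocation by hospital is a separate issue that this change does not address.
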